## **7.2. Laboratory Evaluations**

Laboratory data collected during the study, scheduled and unscheduled, will be analyzed and summarized using qualitative method.

The analysis will be based on values reported in conventional units. When values are below the LOQ, they will be listed as such.

A by-subject listing for laboratory test results will be provided by subject ID number and time point in chronological order for hematology, serum chemistry, coagulation, and urinalysis separately. Values falling outside of the relevant reference range and/or having a severity grade of 1 or higher on the CTCAE severity grade will be flagged in the data listings, as appropriate.

No formal statistical testing is planned.

### **7.2.1. Summaries of Numeric Laboratory Results**

No summaries of numerical laboratory results will be provided.

### **7.2.2. Graded Laboratory Values**

CTCAE version 4.03 will be used for assigning toxicity grades (0 to 4) to laboratory results for analysis. Grade 0 includes all values that do not meet the criteria for an abnormality of at least Grade 1. For laboratory tests with criteria for both increased and decreased levels, analyses for each direction (ie, increased, decreased) will be presented separately. Local labs will be graded based on the central lab normal ranges with in-house macro. In the event where both central and local lab results are collected in the clinical database, baseline flag, worst toxicity and toxicity shift should be derived using both central and local lab results. All central and local laboratory values will be listed.

#### **7.2.2.1. Treatment-Emergent Laboratory Abnormalities**

Treatment-emergent laboratory abnormalities are defined as values that increase at least 1 toxicity grade from baseline at any post-baseline time point, up to 30 days after the last dose of ADX, or if applicable, 5 months after the last dose of nivolumab (whichever is later). If the relevant baseline laboratory value is missing, then any abnormality of at least Grade 1 observed within the time frame specified above will be considered treatment emergent.

#### **7.2.2.2. Summaries of Laboratory Abnormalities**

The following summaries (number and percentage of subjects) for treatment-emergent laboratory abnormalities will be provided by lab test and cohort; subjects will be categorized according to the most severe postbaseline abnormality grade for a given lab test:

- Worst treatment-emergent laboratory abnormalities postbaseline grade (Grade 1 to 4 separately, Grade 3 or 4, and Grade 1 to 4)

For all summaries of laboratory abnormalities, the denominator is the number of subjects with nonmissing postbaseline values up to 30 days after the last dose of ADX, or if applicable, 5 months after the last dose of nivolumab (whichever is later).

A by-subject listing of treatment-emergent Grade 3 or 4 laboratory abnormalities will be provided by subject ID number and visit in chronological order. This listing will include all test results that were collected throughout the study for the lab test of interest, with all applicable severity grades and abnormal flags displayed.

### **7.2.3. Shifts Relative to the Baseline Value**

Shift tables will be presented for each cohort by showing change in CTCAE grade from baseline to the worst post-baseline grade.

### **7.3. Body Weight and Vital Signs**

A by-subject listing of vital signs will be provided by subject ID number and time point in chronological order. High or low values for vital signs will be flagged. Body weight will be included in the vital signs listing, if space permits. If not, they will be provided separately.

### **7.4. Prior and Concomitant Medications**

Medications collected at screening and during the study will be coded using the current version of the World Health Organization (WHO) Drug dictionary.

#### **7.4.1. Prior Medications**

Prior medications are defined as any medications begun before a subject took the first study drug (ADX).

For the purposes of analysis, any medication with a start date prior to the first dosing date of study drug will be considered as prior medication regardless of when the stop date is. If a partial start date is entered the medication will be considered prior unless the month and year (if day is missing) or year (if day and month are missing) of the start date are after the first dosing date. Medications with a completely missing start date will be considered as prior medication, unless otherwise specified.

A summary of prior medications will not be provided.

#### **7.4.2. Concomitant Medications**

Concomitant medications are defined as medications taken while a subject took study drug (ADX). Concomitant medications will be summarized by Anatomical Therapeutic Chemical (ATC) drug class level 2 and preferred name using the number and percentage of subjects for each cohort. A subject reporting the same medication more than once will be counted only once when calculating the number and percentage of subjects who received that medication. The summary will be ordered alphabetically by ATC medical class and then by preferred term in descending overall frequency within each ATC medical class. For drugs with the same frequency, sorting will be done alphabetically.

For the purposes of analysis, any medications with a start date prior to or on the first dosing date of study drug and continued to be taken after the first dosing date or started after the first dosing date but prior to or on the last dosing date of study drug will be considered concomitant medications. Medications started and stopped on the same day as the first dosing date or the last dosing date of study drug will also be considered concomitant. Medications with a stop date that is prior to the date of first dosing date of study drug or a start date that is after the last dosing date of study drug will be excluded from the concomitant medication summary. If a partial stop date is entered, any medication with the month and year (if day is missing) or year (if day and month are missing) prior to the date of first study drug administration will be excluded from the concomitant medication summary. If a partial start date is entered, any medication with the month and year (if day is missing) or year (if day and month are missing) after the study drug stop date will be excluded from the concomitant medication summary. Medications with completely missing start and stop dates will be included in the concomitant medication summary, unless otherwise specified. Summaries will be based on the Safety Analysis Set. No formal statistical testing is planned.

All prior and concomitant medications (other than per-protocol study drugs) will be provided in a by-subject listing sorted by subject ID number and administration date in chronological order.

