Subjects who discontinue andecaliximab for reasons other than disease progression may continue to receive anti-cancer agent treatment (SP, SOX, or nivolumab) until disease progression.

If the subject was not receiving andecaliximab at the time disease progression was documented (eg, due to reversible toxicity), after discussion with the medical monitor, andecaliximab may be re-started if the criteria for resuming treatment as described in Section 5.3.1.1 are met and the investigator feels it is in the subject's best interest to do so.

Dose delay of andecaliximab due to holidays, site closures and subject availability may be permitted after discussion with the medical monitor. The reason for interruption or delay should be documented in the subject's study record.

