5.4. Prior and Concomitant Medications

At Screening, all medication taken up to 28 days prior to the screening visit will be recorded on the eCRF. At each study visit, the site will capture any and all medications taken by the subject since the last visit or during the visit (as applicable). Concomitant medications include prescription and non-prescription medications, pre-infusion medications (eg, anti-emetics), and vitamins and minerals.

In addition, supportive therapies given during the course of the study (eg, blood transfusion, growth factor) should be collected and recorded on the eCRF.

During the course of the clinical trial, subjects are anticipated to continue the use of prescribed medications identified during screening procedures, consistent with the study inclusion and exclusion criteria.

Non-study anticancer chemotherapy or immunotherapy (approved or investigational) is not permitted during the trial. If administered, the subject may be removed from the trial.

Inhaled steroids and short courses of oral steroids for anti-emesis or as an appetite stimulant are allowed; however, chronic daily treatment with oral corticosteroids (dose of > 10 mg/day prednisone equivalent) are not allowed.

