#### **7.1.5. Treatment-Emergent Adverse Events**

##### **7.1.5.1. Definition of Treatment-Emergent Adverse Events**

Treatment-emergent adverse events (TEAEs) are defined as 1 or both of the following:

- Any AEs with an onset date on or after the date that ADX and if applicable, nivolumab was first administered and no later than 30 days after permanent discontinuation of ADX, or if applicable, 5 months after permanent discontinuation of nivolumab (whichever is later).
- Any AEs leading to premature discontinuation of ADX and if applicable, nivolumab.

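### The concomitant medication summary stops at the last andecaliximab infusion, while the SAP's other safety summaries run on for 30 days or 5 months

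*SAP*

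**What the plan says.** **Medications in the SAP.** SAP 7.4.1 treats a drug as prior if it starts before the first ADX dose. SAP 7.4.2 treats it as concomitant if it was already in use at the first dose and continued, or if it was "started after the first dosing date but prior to or on the last dosing date of study drug will be considered concomitant medications". A drug with "a start date that is after the last dosing date of study drug will be excluded from the concomitant medication summary". On the listing, 7.4.2 says: "All prior and concomitant medications (other than per-protocol study drugs) will be provided in a by-subject listing".

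**Other safety data in the SAP.** SAP 7.1.5.1 counts an adverse event (AE) as treatment-emergent (TEAE) if it begins "no later than 30 days after permanent discontinuation of ADX, or if applicable, 5 months after permanent discontinuation of nivolumab (whichever is later"). It also counts any AE that led to stopping ADX. The same end date is used for the death categories (7.1.6.2), laboratory abnormalities (7.2.2) and ECGs (7.5).

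**Protocol.** Protocol 8.6 says that safety data up to this end date will be summarised. Protocol 5.3.1.1 allows the partner treatment to go on without ADX: "Subjects who discontinue andecaliximab for reasons other than disease progression may continue to receive anti-cancer agent treatment (SP, SOX, or nivolumab) until disease progression". Protocol 5.4 requires that "supportive therapies given during the course of the study (eg, blood transfusion, growth factor) should be collected and recorded on the eCRF". Medications are reviewed at the 30-day visit (6.10.1) and, in Cohort 4, at the 5-month visit (6.10.2). Drugs used to treat a serious AE go on the concomitant medication section of the eCRF (7.3.2.1).

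**The concern.** For a drug infused every 2 or 3 weeks, the last dosing date is one day, and exposure and toxicity continue beyond it. If a toxicity appears between infusions and ADX is never resumed, the previous infusion becomes the last dosing date. Any supportive drug started for that toxicity then falls after the cut-off. The same applies to supportive treatment begun while a subject continues SP, SOX or nivolumab alone, and to treatment of a late event after nivolumab.

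At stake is the completeness of the safety description. The AE is counted, but the steroid, growth factor or other supportive drug started for it is missing from the medication summary. The data are collected and would simply not be summarised. It is also unclear whether the listing would show them.

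**Working it through.** The plan states no figure on this point, so the check is to apply its date rules to example subjects.

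**Inputs**
- F, L: study day of the first and last ADX dose. N: study day of the last nivolumab dose.
- s: start day of the drug. For the illustration, the AE is assumed to begin on the same day.
- Prior (SAP 7.4.1): s < F.
- Concomitant (SAP 7.4.2): s ≤ F and continued past F, or F < s ≤ L. A drug started and stopped on day F or L also counts.
- TEAE (SAP 7.1.5.1): F ≤ s ≤ E, where E = L + 30, or in Cohort 4 E = max(L + 30, N + 152).
- The SAP does not convert 5 months to days. I used 5 × 365.25 / 12 = 152.2, taken as 152 (calendar range 150 to 153).

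**Hypothetical cases, all with F = Day 1**

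| Case | L | N | s | E | Prior | Concomitant | TEAE |
|---|---|---|---|---|---|---|---|
| 1. Cohort 1, two doses | 15 | – | 20 | 15+30 = 45 | no | no | yes |
| 2. Cohort 1, one dose | 1 | – | 10 | 1+30 = 31 | no | no | yes |
| 3. Cohort 3, two doses | 22 | – | 35 | 22+30 = 52 | no | no | yes |
| 4. Cohort 4, nivolumab continues alone | 15 | 113 | 60 | max(45, 265) = 265 | no | no | yes |
| 5. Cohort 4, both stopped | 57 | 57 | 150 | max(87, 209) = 209 | no | no | yes |
| 6. Cohort 1, drug given on the last infusion day | 15 | – | 15 | 45 | no | yes | yes |
| 7. Cohort 1, drug started the day before and continued | 15 | – | 14 | 45 | no | yes | yes |
| 8. Cohort 3, late event on SOX alone | 22 | – | 53 | 52 | no | no | no |

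Cases 1 to 5 show the gap. Cases 6 and 7 show what is kept. Case 8 shows that in Cohorts 1 to 3 the mismatch generally lies within 30 days of ADX, because later AEs are not TEAEs unless they led to stopping ADX.

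**Tail after the last ADX dose.** For newly started drugs it is L − L = 0 days. For AEs in Cohorts 1 to 3 it is (L + 30) − L = 30 days. In Cohort 4 it runs to about 152 days after nivolumab.

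**Dependence on whether ADX resumes.** In case 1 the next infusion would be due on Day 29. If it is given, L is at least 29, so s = 20 ≤ L and the same drug is concomitant. If toxicity prevents it, L stays at 15 and the drug is left out.

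**Sensitivity to the AE window.** Protocol 8.6.2 ends TEAEs at 30 days after ADX in every cohort. Under that definition cases 4 and 5 are no longer TEAEs (60 > 45 and 150 > 87), but cases 1 to 3 are unchanged.

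**Incomplete dates.** A partial start date is excluded only if its month or year falls after the ADX stop date. A completely missing start date makes a drug prior. The gap therefore concerns mainly drugs with a known start date.

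**Listing.** The drugs in cases 1 to 5 fit neither class named in the listing sentence. That sentence, however, states no date limit of its own.

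**The case against.** The definition is explicit and coherent: it describes drugs taken while on ADX, and a longer tail is arguably a preference. Protocol Section 8 names no medication analysis, so the link to Protocol 8.6 rests on the SAP placing medications among its safety analyses. The cut-off also applies to everyone at the last dose, including subjects who stop for progression, and drugs already in use by then are kept for all. A longer window has a price: cohorts would be observed for unequal periods, and drugs given for progressing disease would enter the table. All of this stands, and it shapes the fix. It does not explain why medications alone get a 0-day tail when AEs, deaths, laboratory abnormalities and ECGs share a longer one.

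A reader might also infer three stronger things that the documents do not support.

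- **That these drugs vanish from the listing.** Every exclusion in SAP 7.4.2 names the summary only, and Protocol 8.3 plans by-subject listings from each eCRF module. A programmer could properly list every record. The wording is ambiguous, no more.
- **That the primary endpoint is biased.** Protocol 8.1.2 defines it by laboratory tests, physical examination, ECG, vital signs and AE incidence. In the combination cohorts, Protocol 3.3 judges tolerability by ADX interruptions and dose modifications. Medication use belongs to neither.
- **That an AE reported as treated would have no matching drug.** No SAP table or listing reports whether an AE was treated, or links AEs to medications.

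**Conclusion.** The point holds as a gap in descriptive safety reporting. Read literally, SAP 7.4.2 leaves out of the summary any drug with a known start date after the last ADX infusion, even when the AE it treats is counted. Supportive drug use is therefore understated, notably where toxicity ended ADX. Whether the listing must show these drugs is unclear.

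The firm size is the difference in tails: 0 days against 30 days in Cohorts 1 to 3, and against about 152 days after nivolumab in Cohort 4. The Cohort 4 figure assumes 152 days for 5 months and the SAP 7.1.5.1 window. At the extreme, a subject with a single infusion in Cohorts 1 to 3 has newly started drugs summarised for Day 1 only, against AEs for Days 1 to 31.

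The share of medications or subjects affected cannot be derived. It would be tempting to build one from the 1.61-month median PFS on nivolumab cited in Protocol 1.1.1. That figure comes from nivolumab alone after at least two prior lines, whereas Cohort 4 requires one and allows treatment beyond first progression (Protocol 6.12.9.2). A share of days is also not a share of drugs.

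No test, primary endpoint, sample size or dose decision changes.

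**What to change.** - **Summary.** In SAP 7.4.2, extend the concomitant medication summary to the end of the 7.1.5.1 window, and use the same end date in the partial-date rules.
- **Presentation.** Show drugs started after the last ADX dose separately from on-treatment drugs, so that the unequal cohort windows and drugs given for progression are visible.
- **Listing.** State that it covers every recorded medication, flagged prior, concomitant or post-treatment. A drug may carry both of the first two flags, since 7.4.1 disregards the stop date.
- **Anti-cancer therapy.** Keep post-treatment anti-cancer therapy in its own listing, as SAP 7.6 already does.

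If the sponsor prefers to keep the summary as it is, the listing should still be clarified, and the restriction should be stated in SAP 7.7, which at present declares only the omission of continuous safety summaries.

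The cost is SAP wording, one changed end date in the programming, and one added block in the table. No new data are needed. The remaining drawback is that the post-treatment block will include some drugs given for progressing disease, which is why it should stand apart.

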## **7.5. Electrocardiogram (ECG) Results**

Electrocardiogram (ECG) analysis results are intended to identify meaningful changes in the QT interval. If potential abnormalities of interest are identified, further analyses may be conducted.

ECG data collected up to 30 days after the last dose of ADX, or if applicable, 5 months after the last dose of nivolumab (whichever is later), will be included in the summary analysis.

Analyses of ECG data will be provided by cohort using the Safety Analysis set.

### **7.5.1. Investigator Electrocardiogram Assessment**

A by-subject listing for ECG assessment results will be provided by subject ID number and time point in chronological order.

### **7.5.2. Corrected QT Intervals**

The QT interval (measured in millisecond [msec]) is a measure of the time between the start of the Q wave and the end of the T wave in the heart's electrical cycle. The QT interval represents electrical depolarization and repolarization of the ventricles. The QT interval is affected by heart rate, and a number of methods have been proposed to correct QT for heart rate.

Corrected QT (QTc) intervals will be derived using Fridericia's correction (QTcF) as follows:

$$QT_{cF} = \frac{QT}{\sqrt[3]{RR}}$$

where QT is measured in msec; RR = 60/Heart Rate (beats per min [bpm]) and RR is measured in seconds. Per Gilead data collection standard, ventricular rate (VR) is taken as heart rate and will be used to derive RR.

The maximum postdose QTcF interval values obtained during the study will be summarized within the following categories:

- > 450 msec
- > 480 msec
- > 500 msec

The maximum postdose change in QTcF interval values obtained during the study will also be summarized within the following categories:

- > 30 msec
- > 60 msec

### **7.5.3. PR and QRS Intervals**

The PR interval (measured in msec) is a measure of the time between the start of the P wave (the onset of atrial depolarization) and the beginning of the QRS complex (the onset of ventricular depolarization). The QRS interval measures the duration of the QRS complex. The maximum ventricular rate (VR) and PR and QRS intervals observed during the study will be categorized. The number and percentage of subjects having values in the following ranges will be presented by cohort:

- VR > 100 bpm
- PR interval > 200 msec
- QRS interval > 110 msec

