6.12.6. Electrocardiogram Assessment

For all cohorts, a single 12-lead ECG will be collected at screening, on Day 1 of each cycle, and at the EOS Visit, per standard practice.

The investigator or qualified designee will review all ECGs and retain the tracing with the source documents. Appropriate data will be reported on the eCRF.

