8.6. Safety Analysis

All safety data collected on or after the date that andecaliximab and if applicable, nivolumab was first administered up to 30 days after the last dose of andecaliximab or if applicable, 5 months post-treatment of nivolumab (whichever is later), will be summarized by treatment dose level/cohort. Data for the pre-treatment and post-treatment follow-up period will be included in data listings.

For categorical safety data including incidence of adverse events and categorizations of laboratory data, count and percent of subjects will be summarized. For continuous safety data including laboratory data, sample size, mean, standard deviation, minimum, quartiles, median, and maximum will be summarized.

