8.6.4. Other Safety Evaluations

Similar general approaches to the AE and clinical laboratory data will be utilized to summarize other safety measures.

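### SAP 7.5.3 takes maximum VR, PR and QRS with no postdose restriction or baseline comparison, so the baseline ECG can set the maximum and stable pre-existing abnormalities are counted

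*SAP*

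**What the plan says.** SAP 7.5.3 sets the rule for ventricular rate (VR), PR and QRS: "The maximum ventricular rate (VR) and PR and QRS intervals observed during the study will be categorized". The display is a count: "The number and percentage of subjects having values in the following ranges will be presented by cohort". The limits are VR above 100 bpm, PR above 200 msec and QRS above 110 msec. The section has no postdose qualifier and no change or shift from baseline.

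SAP 7.5.2, immediately before it, treats QTcF differently. For absolute values: "The maximum postdose QTcF interval values obtained during the study will be summarized within the following categories". For comparison with baseline: "The maximum postdose change in QTcF interval values obtained during the study will also be summarized", with rows above 30 and above 60 msec.

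The time window in SAP 7.5 has an upper end only: "ECG data collected up to 30 days after the last dose of ADX", or 5 months after the last nivolumab dose where that applies and is later. Protocol 8.6 supplies a lower end: "All safety data collected on or after the date that andecaliximab and if applicable, nivolumab was first administered". It assigns pre-treatment data to listings. SAP 7.7 declares one departure from the protocol's safety analyses, namely that continuous safety data will not be summarized.

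On the schedule, Protocol 6.12.6 says that "a single 12-lead ECG will be collected at screening, on Day 1 of each cycle, and at the EOS Visit". Protocol 6.3.1, 6.4.1 and 6.4.2 list the Day 1 ECG among the pre-dose procedures for every cohort. Protocol 8.3 defines baseline as the last value before treatment.

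**The concern.** A threshold count in a safety table is useful when it shows what appeared or worsened after exposure. As written, 7.5.3 does not require that. A subject enters a row if any eligible ECG exceeds the limit, including one taken before the drug was given. A subject whose PR or QRS was already long and never changed enters the row as well.

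Two facts raise the stakes somewhat. Protocol 8.1.2 names 12-lead ECGs as a component of the primary safety endpoint. And because SAP 7.7 drops continuous summaries, the 7.5.3 counts are the only planned aggregate of VR, PR and QRS, with no mean change beside them to give context. In cohorts of 6 or 10, a single pre-existing abnormality produces a visible percentage, and a new abnormality would be added to the same row without distinction.

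**Working it through.** The plan gives no figure on this point, so there is none to reproduce. The check sets the rules side by side and then sizes the effect.

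**Step 1: which ECGs can set the maximum.**

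| ECG | SAP 7.5 and 7.5.3 as written | With the Protocol 8.6 window applied |
|---|---|---|
| Screening | Included (no lower limit) | Excluded (before first-dose date) |
| Cycle 1 Day 1, pre-dose | Included | Still included if taken on the dosing date |
| Day 1 of later cycles, EOS | Included | Included, within the upper limit |

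The second row is the residual problem. Protocol 8.6 works by date, while the Cycle 1 Day 1 ECG is pre-treatment by clock time. That ECG is normally the baseline value itself.

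**Step 2: comparison with the SAP's other safety rules.** QTcF uses postdose maxima and postdose change (7.5.2). Laboratory abnormalities are treatment-emergent only if they worsen by at least one grade from baseline (7.2.2.1), are categorized by worst postbaseline grade (7.2.2.2), and are shown as shifts (7.2.3). VR, PR and QRS have none of these features.

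**Step 3: two mechanisms, which need different remedies.**

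- Abnormal before dosing only: counted because a pre-dose ECG can set the maximum. A postdose restriction removes it.
- Abnormal before dosing and unchanged afterwards: counted because nothing is compared with baseline. A postdose restriction alone does not remove it.

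**Step 4: weight of one subject.** Cohort sizes are 6 for Cohort 1 at 800 mg, up to 6 for Cohort 2, and up to 10 for Cohorts 3 and 4 (Protocol 8.9; SAP 1.3). One subject is 1/6 = 16.7% or 1/10 = 10.0% of a row.

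**Step 5: chance that a given row contains at least one subject abnormal before dosing.** Let q be the proportion of subjects above one limit before dosing. The documents do not give q, so the values below are assumptions. With independent subjects, P = 1 − (1 − q)^n.

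| Assumed q | n = 6 | n = 10 |
|---|---|---|
| 2% | 1 − 0.98^6 = 0.114 | 1 − 0.98^10 = 0.183 |
| 5% | 1 − 0.95^6 = 1 − 0.7351 = 0.265 (0.2649, about 26%) | 1 − 0.95^10 = 1 − 0.5987 = 0.401 |
| 10% | 1 − 0.90^6 = 0.469 | 1 − 0.90^10 = 0.651 |
| 20% | 1 − 0.80^6 = 0.738 | 1 − 0.80^10 = 0.893 |

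These are per-row figures, matching the way 7.5.3 reports the three parameters on separate lines. They do not divide the two mechanisms in Step 3. With the Protocol 8.6 window applied, an abnormality seen at screening only drops out, so q then refers to the Cycle 1 Day 1 ECG.

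**The case against.** The strongest reply is that the protocol already governs the matter. Protocol 8.6 sends pre-treatment data to listings, SAP 7.7 does not depart from it, and a programmer who applies it drops the screening ECG. That stands. It narrows the exposure to one pre-dose ECG per subject, and even for that ECG one can argue that it belongs to the pre-treatment period in spite of its date. The text leaves this open; it does not settle it.

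A second reply is that a chronological by-subject ECG listing is planned (SAP 7.5.1). With at most 10 subjects per cohort, a reader can check each flagged subject against the pre-dose tracing. That also stands, and it is the main reason the point is minor. It does not repair the summary percentage.

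A third reply is that absolute-threshold counts are a legitimate descriptive choice in a study without formal testing, and that SAP 7.5 directs ECG analysis at the QT interval, which does have change rows. This weakens any complaint about the absolute QTcF rows. It does not explain why VR, PR and QRS lack the postdose qualifier that appears one section earlier.

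Some stronger readings are tempting, but the documents do not support them:

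- *Pre-treatment abnormalities in general are reported as on-treatment findings.* Protocol 8.6 excludes screening values from summaries, and the SAP never labels this table on-treatment or treatment-emergent.
- *A flag cannot be told apart from a drug effect.* The listing allows that separation.
- *A cohort's table is more likely than not to show a spurious flag.* Pooling the three rows at q = 5% gives 1 − 0.95^18 = 0.603 for n=6 and 1 − 0.95^30 = 0.785 for n=10. That requires independence and equal prevalence across parameters, and it merges rows that are reported separately.
- *The SAP departs from Protocol 8.6.4 without declaring it.* That section says only: "Similar general approaches to the AE and clinical laboratory data will be utilized to summarize other safety measures". It prescribes no treatment-emergent definition for ECGs.
- *Eligibility places no cardiac restriction.* There is no numerical VR, PR or QRS limit, so stable abnormalities can enter. But exclusion 5 bars recent serious uncontrolled arrhythmia, and exclusion 1 bars clinically significant disorders that pose a risk.

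**Conclusion.** The defect is real and small. SAP 7.5.3 omits both the postdose restriction and the baseline comparison that SAP 7.5.2 applies to QTcF. With Protocol 8.6 applied, the Cycle 1 Day 1 pre-dose ECG can still set the maximum because the window opens by date. A stable pre-existing abnormality is counted whichever way the window is read.

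One affected subject is worth 16.7 points (n=6) or 10 points (n=10). The chance of at least one in a given row is about 26% or 40% at a 5% baseline prevalence. That prevalence is assumed, and the chance is about 11% or 18% at 2% and 47% or 65% at 10%. The weight of one subject depends only on cohort size; the probabilities depend on the assumed prevalence and on independence between subjects.

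No hypothesis test, sample size, DLT rule or dose decision uses this table. It is a minor correction that makes one component of the primary safety endpoint readable from its summary.

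**What to change.** In SAP 7.5.3, replace the phrase about values observed during the study with: *maximum postdose value (after the first ADX infusion, within the SAP 7.5 window)*. Anchoring to the first infusion matters in two ways. A date-based anchor would let the Cycle 1 Day 1 pre-dose ECG back in. And the Day 1 ECGs of later cycles, although taken before that day's infusion, should remain eligible.

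For VR, PR and QRS, show baseline category (last pre-dose ECG) by worst postdose category, by cohort. Subjects already above a limit at baseline then appear separately from those who newly cross it. The same display for the absolute QTcF categories is optional, because QTcF already has change rows.

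The cost is a wording change and one slightly larger table. The baseline ECGs are already collected under Protocol 6.12.6, so no new data are needed.
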